3.0 Introduction

The Adherence to biological medication in Rheumatoid Arthritis (RA), Psoriatic Arthritis (PsA), Ankylosing Spondylitis (AS), plaque psoriasis (PsO), Crohn's disease (CD) and ulcerative colitis (UC):

As there exist a lot of variations in the definitions and methodologies of measurement used to characterize adherence - compliance and persistence - first of all it is important to provide a definition for these terms. Compliance or more precisely medication compliance refers to the extent a patient is passively following the physician's orders as acting in accordance with the prescribed timing, frequency and dosage. It is typically measured as a percentage of total number of doses taken in relation to the time period of observation, during which medication compliance is measured ^{1,2}. In the literature an arbitrary cut-off value of 80% is used to distinguish between compliance and non-compliance although it is not clear what the clinically relevant cut-off point is. It is also understandable that the required drugs which are necessary to achieve an optimal treatment goal may be different for each patient and each drug. Therefore some patients may be well controlled with a standard dosage scheme while other patients may require a more frequent administration. Persistence or more precisely medication persistence is the duration of time from the beginning to the discontinuation of the prescribed therapy and is measured in units of time ^{1,2}. Adherence can be considered as an umbrella term for medication compliance and medication persistence as this term involves both perceptions of taking a medication, namely regularity and consistency ^{1,2}. Poor or non-adherence to a drug is a very important aspect in contributing to inadequate response to or failure of treatment and worsening of the disease. In consequence of an insufficient adherence clinical outcomes will deteriorate and may prompt a physician to further diagnostic procedures and eventually to an unnecessary change in medication³. Clearly this may lead to a longer patient recovery period and increased healthcare costs. This raises the question: how can we improve adherence in those patients who are afflicted with chronic inflammatory diseases like RA, AS, PsA, PsO, CD or UC? The answer is not easy because adherence is a complex phenomenon and it can both be difficult to identify factors associated with nonadherence and applying help in an effective manner. In clinical studies about tight control such factors can be easier identified and patients can therefore be more intensively motivated to be

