5.0 Study Objectives

5.1 Main objectives

The main purpose of this study is to assess patients' adherence attitudes (beliefs) to the maintenance therapy with a scheduled Adalimumab monotherapy or a combination therapy with methotrexate and to investigate whether there are correlations between such beliefs and adherence to maintenance treatment. In order to measure such beliefs the following questionnaire is used:

 Changes in the Beliefs about Medicines Questionnaire (BMQ) at 12 months compared to baseline. In addition, the correlations between beliefs and adherence to treatment will be done at baseline and at 12 months

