6.4 Study Duration

This PMOS has started In RA, PsA and AS in Feb 2013. The study start for PsO, CD and UC was in November 2014. The estimated end of the patient inclusion is September 2016. Each patient will be observed for a period of max.12 months. Follow-up of patients should enable approximately 5 patient visits (including screening = visit 1) during 12 months. For these reasons, the most likely visits are defined as "V1", "V2", "V3", "V4" and "V5" although numbers

Confidential Information No use or disclosure outside AbbVie is permitted without prior written authorization from AbbVie

and dates will depend only on the decision of the physician. A schedule of activities can be found in the next section. According to the standard of care the approximate frequency of the visits will be 3 months. As a result, failure to meet these suggested dates will not constitute a breach of the protocol.

6.5 Study Conduct and Schedule of Activities:

The study will be conducted in a prospective, single-country, multicenter format. The participating investigator will provide the patient with a prescription for HUMIRA[®]40mg syringe or HUMIRA[®]40mg pen, as the patient can select between two available application devices. Depending on a patient's selection, the investigator will also provide him/her the instructions for appropriate use of the HUMIRA[®]40mg pen (please see Appendix-A) or HUMIRA[®]40mg syringe (please see Appendix-B). Patient safety data and information about co-medications other medications or supplements taken for RA, PsA, AS, PsO, CD or UC will be recorded on electronic data report forms (eCRFs) at study enrollment and during their regularly scheduled visits. If treatment with Adalimumab is interrupted, standard practice is to review the patient after a period of 3 months. If the physician decides to permanently discontinue Adalimumabbefore the end of the planned observational period of 12 months, the reason for discontinuation and the new RA, PsA,AS, PsO, CD or UC treatment regimen prescribed, if applicable, will be documented. The next routine follow-up visit will be the termination visit for this patient in the post-marketing observational study.

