There is no recommendation regarding an appropriate amount of time for wash out of previous BDMARDs prior to initiating Adalimumab therapy. The determination of an appropriate time to initiate Adalimumab following discontinuation of another BDMARD is at the discretion of the physician. While individual patient variability can affect drug elimination, it is generally felt that a majority of a drug is eliminated after 4 to 5 drug half-lives. The health care professional may wish to consider this in determining the appropriate time to initiate Adalimumab therapy. Health care providers should use their knowledge of TNF α biology and best clinical judgment when determining an appropriate washout period of previous BDMARD therapy. AbbVie Austria's recommended wash out periods are: Etanercept received > 3 weeks (21 days) before 1st

_ 10

Adalimumab application Infliximab received > 8 weeks (56 days) before 1st Adalimumab

application

Schedule of Activities

ACTIVITIES	VISIT 1	VISIT 2	VISIT 3	VISIT 4	VISIT 5	EARLY
	SREENING					TERMI-
						NATION
TIME	Month 0	Month 3	Month 6	Month 9	Month 12	
Inclusion /Exclusion Criteria	x		57			
Written authorization to use data	X					
Patient demographics ^a	x		2			
TB: Chest X-ray	x					
TB: IGRA test	x		3			
TB: PPD skin test ¹	х					
ESR	x	x	X	X	X	x
CRP	X	X	X	X	X	х
RADAI ^c	x	x	x	x	x	x
BASDAI ^d	x	x	x	x	x	x
PASI ^e	x	x	x	X	x	x
Harvey-Bradshaw Index (HBI) ^f	x	x	x	x	x	x
Partial Mayo Score ^g	x	x	x	x	x	x
Beliefs about Medicines Questionnaire (BMQ)	x				×	x
Morisky Medication Adherence Scale (MMAS)		x	x	X	x	x
Treatment Satisfaction Questionnaire for Medication (TSQM)		x	x	x	x	x
Concomitant treatment	x	X	X	X	X	x
Adalimumabapplication ^b	x	X	x	x	X	x
Final Statement ^h					X	x

a. Patient demographics: year of birth, gender, race, disease, duration of RA,PsA,AS and previous as well as concomitant treatment

b. Adalimumabadministration: at screening information about dosing frequency and date of first as well as any further applications.

c. for RA and if reasonable for PsA, only

- d. for patients with AS only
- e. for patients with PsO only
- f. for patients with CD only
- g. for patients with UC only

Confidential Information

No use or disclosure outside AbbVie is permitted without prior written authorization from AbbVie

_ 11

abbvie

Adalimumab P13-562 Protocol

- h. Final statement shall also include a statement about pain-management with respect to a potential influence of adalimumab

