All serious adverse events (SAEs) will be reported to AbbVie until 70 days following intake of the last dose of physician-prescribed Adalimumab treatment.

If the physician decides to permanently discontinue Adalimumab this visit will be the termination visit for the patient in the post-marketing observational study.

6.6 **Product Supply**

Since this is a post-marketing observational study, Adalimumabis not supplied by AbbVie. All treatments must be prescribed in accordance with the authorization and local reimbursement guidelines.

Confidential Information

Study treatment:

All regimens will be prescribed according to international and national guidelines for treating RA, PsA, AS, PsO, CD or UC. Adalimumab will be prescribed according to the standard dosing regimen as detailed in the released SPC.

Permitted treatments:

In the context of an observational non-interventional study, the physician is free to initiate any co-prescriptions according to his or her own judgment, although he or she will pay attention to treatments interacting with Adalimumab.

Prohibited treatments:

In the context of an observational study the physician may prescribe according to his or her own judgment although he or she is reminded that Adalimumab must be associated with neither IL-1-antagonists (Anakinra) nor abatacept.

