11.0 Data Analysis Plans

11.1 End points

11.1.1 **Primary end point**

Patients' adherence attitudes (beliefs) to maintenance therapy with a scheduled Adalimumab monotherapy or a combination therapy with methotrexate will be assessed at baseline (visit 1 =screening) and at the end of the study at visit 5. Furthermore it shall be investigated whether there are correlations between such beliefs and adherence to maintenance treatment.

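### The baseline belief-adherence correlation has no same-visit MMAS, the month-12 one mainly describes patients who persisted, and beliefs are never related to persistence

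*Combined protocol and SAP*

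**What the plan says.** Section 5.1 promises that "the correlations between beliefs and adherence to treatment will be done at baseline and at 12 months". Section 11.1.1 repeats the question: "Furthermore it shall be investigated whether there are correlations between such beliefs and adherence to maintenance treatment". It states that beliefs "will be assessed at baseline (visit 1 =screening) and at the end of the study at visit 5". Neither section says which adherence variable is meant.

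Section 4.0 introduces the BMQ for beliefs and the MMAS to find patients at risk of non-adherence. Section 6.5.1 scores the MMAS from 0 (non-adherent) to 4 (adherent). Section 5.2 lists MMAS change from month 3 to month 12 as a secondary objective. In the Schedule of Activities the BMQ is taken at visits 1 and 5 and the MMAS at visits 2 to 5; both are also taken at early termination.

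The Introduction (3.0) sets the definitions: "Adherence can be considered as an umbrella term for medication compliance and medication persistence", and "Persistence or more precisely medication persistence is the duration of time from the beginning to the discontinuation of the prescribed therapy".

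On permanent discontinuation, section 6.5 says: "The next routine follow-up visit will be the termination visit for this patient in the post-marketing observational study". Section 6.5.2.3 agrees: "If the physician decides to permanently discontinue Adalimumab this visit will be the termination visit for the patient in the post-marketing observational study".

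Section 11.1.2 measures time on adalimumab in the context of tolerability. Appendix D records injection dates, a discontinuation date and a reason. Section 11.2 compares compliance by patient characteristics without naming beliefs. It allows no working hypothesis and promises a data analysis plan, which is not among the documents.

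**The concern.** The main purpose is to learn whether beliefs go with adherence to maintenance treatment. Three things stand in the way.

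- **Baseline.** The BMQ has a visit-1 value and the MMAS does not. One of the two promised correlations therefore lacks its natural partner at that visit.
- **Month 12.** Apart from early termination, visit 5 is the only scheduled visit with both questionnaires. Most patients who stop before visit 4 leave before visit 5. A visit-5 correlation is conditional on having stayed, and staying is itself part of adherence as the protocol defines it.
- **Persistence.** The data needed to relate beliefs to time on drug are collected, but no stated analysis uses them for that purpose.

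The report could therefore answer the main question only for self-reported medication-taking among persisters, and read as if it covered everyone who started.

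**Working it through.** **1. The schedule, side by side**

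| | V1 | V2 | V3 | V4 | V5 | Early termination |
|---|---|---|---|---|---|---|
| BMQ | yes | no | no | no | yes | yes |
| MMAS | no | yes | yes | yes | yes | yes |

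No same-visit pair exists at V1. The nearest baseline pairing is V1 BMQ with V2 MMAS.

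**2. Patients behind each result**

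Planned n = 80 + 30 + 30 = 140 (section 6.2). The documents give no stopping rate. Assume that a share p = 10%, 25% or 40% stop, evenly over 12 months.

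- Stops: 140p = 14, 35, 56.
- On treatment at V2: 140 − 140p × 3/12 = 136.5, 131.25, 126.
- With a V5 visit, if only those stopping after month 9 still reach it: 140 − 140p × 9/12 = 129.5, 113.75, 98.
- With a V5 visit, if no stopper reaches it: 140(1 − p) = 126, 105, 84.

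**3. What conditioning on V5 can do to the correlation**

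Assume bivariate normal scores, with beliefs oriented so that higher is more favourable, and true r = 0.30. No stopper has V5. In the extreme case stopping is fully determined by the score in question. If the lowest share p is removed, that score's remaining variance is v = 1 + qλ − λ², where q is the normal quantile at p and λ = φ(q)/(1 − p). This gives v = 0.712, 0.535, 0.422.

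*Stopping follows adherence alone:* r′ = 0.30√v / √(0.91 + 0.09v) = 0.26, 0.22, 0.20.

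*Stopping follows beliefs and adherence equally:* the standardised sum is truncated, so r′ = (0.65v − 0.35)/(0.65v + 0.35) = 0.14, 0.00, −0.12.

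*The same, but the stopping tendency correlates only 0.7 with that sum:* replace v by 1 − 0.49(1 − v) = 0.859, 0.772, 0.717. Then r′ = 0.23, 0.18, 0.14.

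Simulation with 4 million pairs gives the same values. If stopping is unrelated to either score, r′ stays at 0.30.

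| Stop | n at V5 | 95% half-width at r = 0.30 | Adherence alone, extreme | Both, extreme | Both, link 0.7 |
|---|---|---|---|---|---|
| 10% | 126 | 0.16 | 0.26 | 0.14 | 0.23 |
| 25% | 105 | 0.175 | 0.22 | 0.00 | 0.18 |
| 40% | 84 | 0.20 | 0.20 | −0.12 | 0.14 |

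If stop times are even and a quarter of stoppers reach V5, the extreme equal-dependence case gives 0.19, 0.14 and 0.15.

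**4. What a persistence analysis could deliver**

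The approximate 95% CI for the hazard ratio per SD of baseline BMQ is the estimate divided and multiplied by exp(1.96/√d), where d is the number of stops. For d = 14, 35, 56 the factor is 1.69, 1.39, 1.30. A simulated Cox model stratified 80/30/30 gives 1.71, 1.40, 1.31. If a further 10% are lost and censored, it gives 1.74, 1.41, 1.32.

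**The case against.** **The MMAS is plainly the adherence measure.** This largely stands. A reader might infer that the protocol has no adherence instrument, but sections 4.0 and 6.5.1 do not support that. The gap is that the MMAS is not assigned to the primary correlation. Other candidates exist: percentage of doses taken (3.0), the final adherent/non-adherent statement (Appendix D) and time on treatment (11.1.2). Section 5.2 already uses month 3 as the MMAS reference, which makes a V2 pairing natural. None of this supplies an MMAS value at V1.

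**Stoppers do have data.** This is true. BMQ and MMAS are scheduled at early termination, so it would be wrong to say that stoppers go unmeasured. What is missing is a rule for using those values. Section 11.1.1 points to V5 as the end-of-study value, and that reading should be kept.

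**The study is descriptive and an analysis plan is promised.** Both are true, and that plan may settle these points. A descriptive estimate still needs a defined variable, visit pair and patient set.

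**Stopping may be the physician's decision.** This stands. A stop is not by itself poor medication-taking, so a persistence result describes and does not explain.

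**The selection effect is too small to matter.** A reader might infer that any shift lies within sampling error and that bias can be set aside. That holds in the cases tried where stopping depends on adherence alone. It fails in the extreme equal-dependence case: at 40% stopping the shift is 0.42 against a half-width of 0.20. The protocol's own premise, in the Introduction, is that concerns about treatment can lead patients not to take it. The opposite inference, that the V5 correlation is known to be badly biased, is not supported either. With a link of 0.7 the largest shift is 0.16, below the half-width.

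**Conclusion.** The point holds as an under-specified primary analysis with two concrete consequences. With the MMAS as the adherence measure, the baseline correlation cannot be computed at a single visit, and the V5 correlation is conditional on persistence. Separately, part of the protocol's own definition of adherence is not related to beliefs in any stated analysis.

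The schedule, exit and definition parts rest on the text alone. The size of any distortion rests on assumptions, because the documents give neither a stopping rate nor a correlation. At true r = 0.30 with no stopper reaching V5, results range from no change to a reversed sign, depending on what drives stopping. Bias can be neither asserted nor dismissed from these documents. Confidence is medium, because the data analysis plan was not available.

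**What to change.** In 11.1.1 and 11.2, or in the promised data analysis plan:

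1. Name the MMAS as the measure of self-reported adherence and state which BMQ score is used. Section 6.5.1 describes a Specific-plus-General total, while the Appendix D form prints the 10 Specific items. Replace the baseline correlation by V1 BMQ with V2 MMAS. Keep V5 BMQ with V5 MMAS, labelled as applying to patients still in the study at V5.
2. Add a descriptive analysis in all enrolled patients of baseline BMQ against time from first adalimumab dose to permanent discontinuation. Use delayed entry at V1 where the first dose came earlier, since section 6.1.1 allows prescription up to 30 days before screening. Stratify by indication group and report the hazard ratio with its 95% CI and no test. State which Appendix D field defines the stop: the early-termination date also serves loss to follow-up and death, and the final-visit form has its own field for stopped therapy. State how loss to follow-up and death are handled.
3. Keep V5 as the main end-of-study BMQ value. Show early-termination BMQ and MMAS separately, because they come at varied times and may be answered after stopping. Give n for every result.

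The cost is plan text and analysis time. The dates and reasons are already in the eCRF, and section 9.0 already provides for queries on inconsistent data. The limits are that with an assumed 14 to 56 stops the hazard ratio is imprecise (CI factor about 1.7 to 1.3) and supports only one covariate. The recorded reasons will also not cleanly separate patient from physician decisions.

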5.2 Secondary objectives

- Changes in the Morisky Medication Adherence Scale (MMAS) at 12 months compared to month 3,
- Changes of the Treatment Satisfaction Questionaire for Medication (TSQM) over time,
- Changes in Rheumatoid Arthritis Disease Activity Index (RADAI) in patients with RA and if reasonable in patients with PsA,
- Changes in Bath Ankylosing Spondylitis Disease Activity Index (BASDAI) in patients with AS,
- Changes in Psoriasis Area and Severity Index (PASI) in patients with plaque psoriasis,
- Changes in Harvey-Bradshaw Index (HBI) for patients with CD,
- Changes in Partial Mayo Score (**PMS**) for patients with UC,
- Changes of the C-reactive protein (CRP) over time
- Changes of the Erythrocyte sedimentation rate (ESR) over time

6.0 Investigational Plan

6.1 Selection of Study Population

The study P13-562 is a non-interventional, observational study in which HUMIRA[®] is prescribed in the usual manner in accordance with the terms of the local marketing authorization with regards to dose, population and indication. The assignment of the patient to a HUMIRA[®] containing regimen has to be decided in advance and has to be current practice. The prescription of HUMIRA[®] is clearly separated from the decision to include the patient in this study! No additional procedures (other than standard of care) shall be applied to the patients.

It is planned to enroll approximately 140 patients in total. All patient data entered in the patient's data report form (CRF) will be forwarded - without naming the patient - for evaluation to AbbVie. In order to maintain patient confidentiality, the patient's age in year, gender and race will be documented in the CRF. The patients must provide written authorization to the investigator to use and/or disclose personal and/or health data before entry into study P13-562.

6.1.1 Inclusion Criteria

- Patients aged ≥ 18 years with RA, PsA, AS, PsO, CD, or UC that have been prescribed adalimumab in accordance to physician's clinical decision and according to local guidelines, up to 30 days prior to screening.
- Patients must fulfil international and national guidelines for the use of a BDMARD in RA,
 PsA, AS, PsO, CD, or UC (Chest X-ray and IGRA* interferon gamma release assay or
 PPD-skin test negative for tuberculosis). *Please see also APPENDIX-C!

In addition one of the following criteria must be fulfilled:

- Unsatisfactory DMARD response defined as failure to treatment with at least two DMARDs including Methotrexate in patients with RA or PsA
- Unsatisfactory NSAID response in patients with **AS** or unsatisfactory response to prior BDMARDs in patients with **RA** or **PsA** or **AS**.
- Unsatisfactory response to or contraindication to, or intolerance to other systemic therapy including cyclosporine, methotrexate or PUVA in patients with PsO.Unsatisfactory response

8

Confidential Information

abbvie Ac

despite a full and adequate course of therapy with a corticosteroid and/or an immunosuppressant; or intolerance or medical contraindications for such therapies in CD.

• Unsatisfactory response to conventional therapy including corticosteroids and 6mercaptopurine (6-MP) or azathioprine (AZA), or intolerance to or medical contraindications for such therapies in UC.

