6.1.2 Exclusion Criteria

The following patients will not be included in this observational study:

- Patients who are not covered in the latest version of the HUMIRA syringe[®] SPC and HUMIRA Pen[®] SPC;
- Patients participating in another study program or clinical trial.
- Patients who have been treated with Adalimumab before.-

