6.5.2 Description of the Visits

6.5.2.1 Inclusion visit

Patients will be documented according to the following procedure: demographics (year of birth, gender, disease and disease duration, results of Chest X-ray and a highly specific interferon- γ -release assay [IGRA] or PPD-test for Tb-screening and RA, PsA, AS, PsO, CD or UC treatment in the past), ESR, CRP; Beliefs about Medicines Questionnaire (BMQ), concomitant treatment other medication or supplement, start of Adalimumab application will be documented in the appropriate eCRF.

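### Visit 1 is the baseline, but the protocol never places it before the first adalimumab injection, so an on-treatment baseline is possible and would go undetected

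*Combined protocol and SAP*

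**What the plan says.** Section 11.1.1 states that beliefs "will be assessed at baseline (visit 1 =screening) and at the end of the study at visit 5", and Section 5.1 makes the comparison a main objective: "Changes in the Beliefs about Medicines Questionnaire (BMQ) at 12 months compared to baseline". For the disease indices, CRP and ESR no baseline is named. Section 5.2 asks for their changes, and the Schedule of Activities has them measured at Visit 1 and at every later visit, so Visit 1 is the implied starting point.

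Five places bear on whether treatment may already have begun at Visit 1:

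- Section 6.1.1 admits patients prescribed adalimumab "according to local guidelines, up to 30 days prior to screening".
- Section 6.1.2 excludes "Patients who have been treated with Adalimumab before", with no reference time.
- Section 6.5 says "The participating investigator will provide the patient with a prescription for HUMIRA", which puts the prescription inside the study.
- Footnote b of the Schedule of Activities asks for "at screening information about dosing frequency and date of first as well as any further applications".
- Section 6.5.2.1 says that at the inclusion visit "start of Adalimumab application will be documented in the appropriate eCRF", without saying whether this comes before or after the questionnaire and laboratory values.

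Section 6.1 adds that the treatment decision is made in advance and kept separate from the decision to enrol.

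**The concern.** A change score is easiest to interpret when its starting value was taken before treatment. Here a prescription that precedes Visit 1 is an expected route into the study. The drug is not supplied by the sponsor (Section 6.6) and can be self-administered (Section 4.0), and nothing asks the patient to wait for Visit 1. The protocol does tie other items to the first application: the skin-test window, the chest X-ray and the washout of earlier biologics. It sets no such anchor for the baseline assessments.

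If some Visit 1 values are taken after one or more injections, the change in disease activity and inflammation markers omits whatever improvement had already occurred. The baseline BMQ, which also enters the planned correlations with adherence, would then mix attitudes before treatment with early experience of it. With 28 sites (Section 6.2) and no monitoring (Section 9.0), sites could read the criteria differently. The plan has no tabulation that would show whether they had.

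**Working it through.** The protocol states no figure for this point, so there is none to reproduce. The check is a reading of the text, followed by a calculation of scale.

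**1. Two readings of the exclusion.** If Section 6.1.2 means never treated before screening, every Visit 1 value is pre-treatment and the issue disappears. If it means never treated before the current prescription, Section 6.1.1 allows up to 30 days on drug at Visit 1. Neither section says which is meant. Section 6.5, footnote b and Section 6.5.2.1 do not settle it, because none orders the first application against the Visit 1 assessments.

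**2. Endpoints exposed.** According to the Schedule of Activities, BMQ, RADAI, BASDAI, PASI, HBI, PMS, CRP and ESR have a Visit 1 value and are exposed. MMAS and TSQM are first collected at month 3, and Section 5.2 states the MMAS comparison as "Changes in the Morisky Medication Adherence Scale (MMAS) at 12 months compared to month 3". Both are unaffected.

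**3. Most exposure the window could allow.** Suppose the first injection falls on the day of prescription, 30 days before Visit 1. Under the standard regimens in Section 4.0:

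- RA, PsA, AS: days 0, 14, 28, which is 3 dosing dates
- Plaque psoriasis: days 0, 7, 21, which is 3 (the next would be day 35)
- Crohn's disease and ulcerative colitis: days 0, 14, 28, which is 3

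This is a ceiling for those schedules. It leaves aside the weekly dosing that the documents mention for some patients. With the stated half-life of 10 to 14 days, 30 days is 30/14 = 2.1 to 30/10 = 3.0 half-lives.

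**4. Dilution of the mean change.** Let D be the mean 12-month change from a pre-treatment value, f the share of patients already dosed at Visit 1, and s the share of D that those patients have already reached. Assume D is the same in both groups. Then

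observed mean change = (1 − f)·D + f·(1 − s)·D = D·(1 − f·s),

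so the proportion lost is f·s. The documents give neither f nor s; all values below are assumptions.

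| f | s | f × s |
|---|---|---|
| 0 (untreated at screening) | any | 0% |
| 10% | 10% | 1% |
| 25% | 20% | 5% |
| 25% | 30% | 7.5% |
| 50% | 40% | 20% |
| 50% | 50% | 25% |
| 75% | 60% | 45% |

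The formula needs early change in the same direction as the 12-month change. That is plausible for disease activity, CRP and ESR in patients who improve early. Nothing in the documents supports it for BMQ, so no percentage is attached to that endpoint.

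**The case against.** The strongest case on the other side is that Visit 1 is pre-treatment by design. A prescription is not an injection. Eligibility is judged at screening, and at that point the natural reading of Section 6.1.2 shuts out anyone already injected. Section 6.5 has the investigator hand over the prescription and the device instructions during the study. Section 6.5.2.1 records the start of application at inclusion. The tuberculosis tests are scheduled at Visit 1, with notes that speak of patients who have yet to start. The analysis is also descriptive (Section 11.2), so no error rate or sample size is at stake.

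Much of this stands. It makes the pre-treatment reading a fair one and is why zero belongs in the range. It does not close the question: tuberculosis results may predate Visit 1, recording a start date does not order it, and no sentence requires assessment before injection.

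A reader might infer from footnote b that patients are expected to be on drug at screening. The footnote does not show this. It belongs to a row marked at every visit, and the matching eCRF page is completed at each visit, so the further applications may simply be dates added later. A reader might also take 5% to 45% as the bias in this study. Those figures follow only from assuming f of 25% to 75% and s of 20% to 60%, and they leave out f = 0.

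**Conclusion.** The point holds as a gap in definition, not as a demonstrated bias. The baseline rule permits an on-treatment starting value, the criteria do not clearly prevent one, and no planned analysis would reveal it. The size is unknown. It is 0% if the exclusion means untreated at screening. Otherwise it is f × s, for example 20% at the assumed f = 50% and s = 40%, with up to three scheduled dosing dates inside the window under the standard regimens. The loss applies to disease indices, CRP and ESR where patients improve early. For BMQ the consequence is an unclear meaning of the baseline score, in an unknown direction; the stronger statement that the BMQ change is understated has no support in the documents. What is affected is the interpretation of descriptive change scores.

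**What to change.** 1. Reconcile Sections 6.1.1, 6.1.2, 6.5 and footnote b of the Schedule of Activities on whether a course already begun at Visit 1 is allowed.

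2. In Section 11.1 and the data analysis plan promised in Section 11.2, use the recorded first-application date to classify each Visit 1 value as before or after first injection. State that a same-day value counts with the former, since dates cannot order events within a day.

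3. Report the number of patients already dosed at Visit 1 and their days since first injection.

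4. Present each change from Visit 1 twice: for all patients, and for those whose Visit 1 was on or before first injection.

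Replacing the baseline by the last value on or before first injection would gain little more. Visit 1 is the only scheduled assessment before month 3, so that definition returns either Visit 1 or a missing value. Showing both analyses keeps everyone in view.

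The cost is a clarified criterion, one derived variable and a second set of descriptive tables. The first-application date is already to be collected. The downside is a smaller restricted sample: at the assumed f = 50%, 140 × (1 − 0.50) = 70 of the planned patients would remain. If nobody was dosed before Visit 1, the two sets coincide and the question is closed.
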